### 12.4 Data analytic plan

***Aim 1:** To determine the impact of low-dose tamoxifen on surrogate endpoint biomarkers of BC risk.*

**Mammographic breast density (MBD).** MBD is the ratio of absolute density to the total breast area. Since participants are randomized, we expect MBD to not differ by treatment status at baseline ( $t_0$ ). However, we will evaluate the success of randomization by examining between group differences in demographic and clinical characteristics (i.e. age, radiation dose, age at radiation exposure), study site, as well as the average MBD of the two breasts (or the available one) at baseline. If imbalance is evident, analysis will take into account the covariates with significant imbalance.

Using an intention-to-treat analysis, the efficacy of low dose tamoxifen in reducing MBD will be compared between patients in the low dose tamoxifen intervention and placebo group by applying the linear mixed effects model for bivariate normally distributed data [103]. All patients with a minimum of baseline ( $t_0$ ) mammographic data will be included in the analysis. MBD data from each breast will be square root transformed (RTMBD) to normality before model fitting. RTMBD for each breast will be modeled by the unstructured mean model using two indicator variables of time. We will assume the effects of time on RTMBD to be the same in both breasts by setting their coefficients equal. Correlation between the breasts will be introduced by assuming a bivariate normal random intercept model with a common fixed effects intercept and breast-specific random effects. Residual errors will be assumed to be bivariate normally distributed with mean zero and non-zero correlation. Unstructured and compound symmetry covariance structures will be considered for residual errors. The fixed effects intercept will be allowed to differ between treatment groups. Interactions of the time indicators with treatment indicator (0 for placebo, 1 for tamoxifen) will be included to allow for treatment

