## 12.5 Power and sample size:

***Aim 1:*** *To determine the impact of low-dose tamoxifen on surrogate endpoint biomarkers of BC risk.*

**Mammographic breast density (MBD):** The primary efficacy endpoint of the trial is MBD. The efficacy of low dose tamoxifen will be examined by comparing the slopes in the longitudinal linear regression of the MBD on time since treatment initiation between the low dose tamoxifen group and placebo control group. For sample size calculation, we let Y, the response, as the mean of the square root of MBD (RTMBD) from both breasts. Because of randomization, we expect no difference between the expected values of Y at t0 between treatments but expect the linear slopes of the two groups to diverge over time, if the intervention is efficacious. Power/sample size calculation was conducted by assuming a linear change in RTMBD over time and various magnitudes of RTMBD difference expected at t2 between the treatment and control groups.

Longitudinal power calculation requires specification of the expected linear trend (thus the expected values of Y at t0, t1, t2) for the controls, the variance/covariance of the repeated measurements, the expected difference in Y at t2 between the treatment groups, and the correlations among repeated measurements. These estimates were obtained from 41 control women in the Puget Sound NSABP P-1 participating sites, [106] 16 pre-menopausal women (median age=50, range=38-50) and 25 post-menopausal women, (median age=57, range=36-74), with data on MBD expressed as a percent breast density at pre-, 1-yr, and 2-yr post-treatment. Although this entire control sample (median age=50, range=36-74) is older than the available CPIR HL cohort (median age=35, range 25-50), based on changes in MBD observed with hormonal fluctuations during the menstrual cycle [66] and after discontinuation of exogenous hormone in postmenopausal women [70], it can be reasonably assumed that estrogen withdrawal associated with menopause has a greater impact on variation in MBD than age alone. Thus, we assumed that the estimates obtained from these women can be applied to the anticipated CAYAC patient control sample.

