The expected RTMBD at the three time points in the pre-menopausal and post-menopausal women in the Puget Sound sample were estimated longitudinally using SAS Proc Mixed with a compound symmetry covariance structure. Square root transformation was used to normalize the distribution. A significant decline in MBD with time was detected. Since the covariance matrices of the pre- and post-menopausal women looked very similar, for simplicity, they were assumed to be equal. To determine the variance/covariances of the MBDs and the expected values at t0, t1, t2 in the anticipated CAYAC sample, 1000 random trials of size n were generated from multivariate normal distributions with parameters estimated from the Puget Sound sample to simulate the CAYAC sample expected to contain 67% pre-menopausal and 33% post-menopausal women. Sixty-seven percent of n were drawn randomly from a multivariate normal distribution with expected MBD of (24.7, 23.57, 22.27) at (t0, t1, t2) as predicted for Puget sound pre-menopausal women, and 33% of n were drawn randomly from a multivariate normal distribution with expected Y of (15.49, 11.99, 13.03) as predicted for post-menopausal women. For each of the 1000 simulated samples, a longitudinal linear model was fitted assuming a compound symmetry structure for the covariance. The average of the 1000 estimates of the linear parameter was used to estimate the expected RTMBD at t0, t1, t2 for the CAYAC control sample.

The expected RTMBDs for CAYAC controls obtained from simulations were used to specify the effect size, defined as the difference between expected values at t2 for the two groups divided by the common sd, in the longitudinal power calculations were conducted using the program RMASS2. [107]. We assumed a Type I error of .05, power of .80, 2-sided test, no attrition over time, linear trend, compound symmetry covariance structure, and a correlation of 0.8 between measurements (estimated from the Puget Sound sample).

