The size of the difference in MBD that can be detected between the low dose tamoxifen and placebo groups at year 2 (t2) are shown in the table below. Column 4 indicates the expected MBD before randomization (at t0). The expected MBDs at t2 for the control and treatment groups are shown in columns 5 and 6, respectively. Column 7 and Column 8 are the % reduction in MBD at t2 relative to t0 in the placebo control group and low dose tamoxifen treatment group, respectively. The last column shows the % reduction in PD in the treatment group at t2 relative to controls.

Placebo (PBO)	Low Dose Tamoxifen (LDTAM)	Power	Exp(MBD) at t0	Exp(MBD) at t2		% reduction in MBD at t2 relative to t0		% reduction in MBD at t2 for LDTAM group relative to PBO
			Both treatment groups	PBO	LDTAM	PBO	LDTAM	
50	50	.8	21.2	18.75	13.42	11.6%	36.5%	28.4%
		.9	"	"	12.68	"	40.0%	32.4%
75	75	.8	21.1	18.67	14.27	"	32.5%	23.5%
		.9	"	"	13.70	"	35.2%	26.6%
100	100	.8	21.2	18.72	14.89	"	29.6%	20.5%
		.9	"	"	14.32	"	32.3%	23.5%
150	150	.8	21.1	18.64	15.47	"	26.8%	17.0%
		.9	"	"	15.00	"	29.1%	19.5%
200	200	.8	21.1	18.67	15.91	"	24.8%	14.8%
		.9	"	"	15.50	"	26.7%	17.0%

If we anticipate the MBD in the low dose tamoxifen group to change from 21.1 at t0 to 14.89 at t2 compared to 18.72 at t2 in controls (in other words, a reduction of ~30% with low dose tamoxifen versus 11.6% with placebo over a 2 year time, or about 20% reduction in MBD with low dose tamoxifen relative to placebo, or an effect size of 0.25 at t2), a sample size of 100 per arm will be able to detect this magnitude of change with 80% power. With 10% attrition at each annual follow-up visit, 115 women per arm (or a total of 230) would be required. Thus, the goal accrual for this trial will be 115 women per arm, for a total of 230 women at t0.

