**Adverse events:** We assume the rate of grade 2-4 toxicities in the placebo group to be low, at 0.5%. At the end of the study, with 94 women in each arm (accounting for 10% attrition per year), the study will have at least 80% power to detect an adverse event rate of 9.1% in the low dose tamoxifen group based on Fisher’s exact test and Type I error=0.05.

**Adherence to therapy:** We will examine the difference in adherence rates of the treatment groups by comparing the percent of pills taken across 8 time points. With 115 women at baseline per arm, assuming a constant adherence rate of 90% in the placebo group and a between-measurement correlation of 0.6 and 2-sided alternative, there will be 80% power to detect an adherence rate of about 77% in the low dose tamoxifen group.

**Voluntary withdrawals:** If the proportion of patients in the placebo arm who withdraws voluntarily by the end of the study is 10%, then with 115 women in each arm at baseline, assuming type I error=0.05, the study will have 80% power to detect a significant difference in the voluntary withdrawal rate in the low dose tamoxifen group if the withdrawal rate in the intervention group is about 28%.

**Safety biomarkers:** We focus here on total cholesterol (TC), anti-thrombin-III (AT-III), bone-specific alkaline phosphatase (BSAP), and urine N-telopeptide crosslinks (NTX). With the proposed sample sizes, the detectable effect size (described earlier) is 0.34. A relatively small % change in mean levels is detectable for TC and AT-III but larger % changes are needed to detect a significant treatment difference at t2 for BSAP and NTX.

Outcome	Assumed levels at t0 for Placebo and Low dose Tamoxifen groups	Detectable levels at t2 (80% power) for Low dose Tamoxifen group	
	Mean ± SD	Mean	Relative % change (from t0)

TC* (mg/dL)	199 ± 45	214.3	8% ↑
AT-III** (%)	100 ± 13.3	95.5	5% ↓
BSAP  (µg/L)	7.7 ± 4.5	6.2	20% ↓
NTX  (nM BCE/mM)	24.4 ± 16.1	18.9	23% ↓

\* Mean obtained from [111], sd obtained from [112]

\*\* per ARUP reference laboratory

Thus, we expect to be able to detect a 5-23% difference in the objective safety biomarkers proposed as secondary endpoints.

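### With the planned arm-specific intercepts, 115 women per arm give about 79% power rather than 80%; one common baseline mean would give about 82% with the same 230 women

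*Combined protocol and SAP*

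**What the plan says.** Section 12.5 powers the comparison of linear slopes in square-root density, averaged over the two breasts. The base calculation is described as "We assumed a Type I error of .05, power of .80, 2-sided test, no attrition over time, linear trend, compound symmetry covariance structure", with "a correlation of 0.8 between measurements (estimated from the Puget Sound sample". The target difference is a density of 14.89 on tamoxifen against 18.72 on placebo at year 2, "or an effect size of 0.25 at t2", for which 100 per arm are said to give 80% power. The step to the final size is a single sentence, "With 10% attrition at each annual follow-up visit, 115 women per arm (or a total of 230) would be required", with no formula. The resulting 230 women are counted at t0.

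Under Aim 2 the same section shows how attrition accumulates: "At the end of the study, with 94 women in each arm (accounting for 10% attrition per year".

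On the baseline, section 12.4 says of the primary mixed model: "The fixed effects intercept will be allowed to differ between treatment groups". The common intercept mentioned in that section is common to the two breasts, not to the two arms. Section 12.5 nevertheless says that, because of randomisation, "we expect no difference between the expected values of Y at t0 between treatments", and section 12.4 opens with the same expectation.

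**The concern.** The base figure of 100 per arm assumes that nobody is lost. Two yearly losses of 10% take 115 to about 93, which is below 100. Women lost before year 2 remain in the mixed model, but with arm-specific intercepts they carry limited information: a woman seen only at baseline helps to estimate her own arm's intercept and adds little to the slope or year-2 contrast. It is therefore fair to ask whether 115 per arm still delivers the stated power.

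Two things are at stake. One is the accuracy of the power statement. The other is whether the model makes full use of the baseline mammograms, which every randomised woman will have.

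**Working it through.** **Inputs** (section 12.5): two-sided alpha 0.05; effect 0.25 SD at year 2; correlation 0.8 with compound symmetry; 1:1 allocation; 115 per arm at t0; 10% of those remaining lost at each visit. Retention is therefore 100/90/81%: 81% have all three visits, 9% have t0 and t1, and 10% have t0 only. Variances are in units of SD².

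**1. The base row reproduces.** √18.72 − √14.89 = 0.468, so an effect of 0.25 implies an SD of about 1.87. With three equally spaced visits and compound symmetry, the slope contrast is Y2 − Y0, with variance 2(1 − 0.8) = 0.4. At 100 per arm the between-arm variance is 2 × 0.4/100 = 0.0080. Then 0.25/√0.0080 = 2.795, and power = Φ(2.795 − 1.960) = 79.8%. The unrounded effect 0.2506 gives 80.0%.

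**2. The 115 reproduces by an approximation.** Divide each visit's variance by its retained fraction, and each covariance by the square root of the product of the two fractions:

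1 + 1/0.81 − 2 × 0.8/√0.81 = 1 + 1.235 − 1.778 = 0.457

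N = 2 × 0.457 × (1.960 + 0.842)²/0.25² = 114.7, i.e. 115 (power 80.1%).

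With monotone dropout this weighting overstates the covariance between visit means, so it is slightly optimistic.

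**3. Exact information, separate intercepts.** For a woman with k visits at times 0, …, k−1, compound symmetry gives the following information on (intercept, slope):

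- intercept: k/(0.2 + 0.8k)
- cross term: Σt/(0.2 + 0.8k)
- slope: 5[Σt² − 0.8(Σt)²/(0.2 + 0.8k)]

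| Visits | Share | Intercept | Cross | Slope |
|---|---|---|---|---|
| 3 | 0.81 | 1.154 | 1.154 | 11.154 |
| 2 | 0.09 | 1.111 | 0.556 | 2.778 |
| 1 | 0.10 | 1.000 | 0 | 0 |
| Weighted mean | | 1.135 | 0.985 | 9.285 |

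Slope information per woman after estimating the arm's own intercept: 9.285 − 0.985²/1.135 = 8.430. The year-2 effect is twice the slope, so its between-arm variance is 2 × 4/(115 × 8.430) = 0.00825. Then 0.25/√0.00825 = 2.752, and power = Φ(0.792) = **78.6%**.

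**4. Exact information, common baseline mean.** With equal arms and a shared intercept, the cross terms cancel in the slope difference and the full 9.285 is kept. The variance is 8/(115 × 9.285) = 0.00749. Then 0.25/√0.00749 = 2.888, and power = Φ(0.928) = **82.3%**. In sample-size terms this is worth 115 × 9.285/8.430 ≈ 127 women per arm under the present model.

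**5. Year-2 contrast and sensitivity.** The year-2 contrast with unstructured means has variance 0.00827 (separate) or 0.00758 (common).

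| Setting, 115 per arm | Separate intercepts | Common baseline |
|---|---|---|
| Slope, effect 0.25 | 78.6% | 82.3% |
| Slope, effect 0.2506 | 78.8% | 82.5% |
| Year 2, effect 0.25 | 78.5% | 81.9% |
| Slope, retention 100/90/80% | 78.2% | 82.0% |
| Slope, correlation 0.7* | 79.0% | 84.8% |
| Slope, correlation 0.9* | 78.5% | 80.3% |

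*Effect rescaled so that 100 complete women per arm still give 80%.

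For 80% power at effect 0.25, separate intercepts need about 120 per arm. A common baseline needs 109 (slope) or 110 (year 2).

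**The case against.** **A longitudinal attrition formula gives 115.** This stands. The software reference cited in section 12.5 concerns, by its title, sample size for longitudinal designs with attrition, and step 2 recovers 115. The documents do not show the formula, so the match is inferred. It is still enough to reject the reading that 115 is an arithmetic mistake.

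**Fewer than 100 women reach year 2.** A reader might infer that 100/0.81, i.e. 124 per arm, are needed, or that power is only the 77% given by 93 completers. The documents do not support this. Section 12.4 keeps every woman with a baseline mammogram in the analysis, and both figures discard the non-completers.

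**The gap is trivial.** For the shortfall alone this is largely right. With the effect held at 0.25, a correlation of 0.75 gives 69.3% and 0.85 gives 88.7% with separate intercepts, and the planning values come from 41 older control women. The gain from a common baseline does not depend on these values being exact: the same two correlations give 74.6% and 90.8%.

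**Section 12.2 expects 230 evaluable subjects.** Section 10.0 defines evaluable as completing at least one year. If all 230 did so and 10% were lost in year 2, separate intercepts would already give 82.3% for the slope. But section 12.5 ties its power to 230 women at t0, and the Schema has 230 randomised. The two counts need reconciling; the evaluable count does not settle the matter.

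**Arm-specific intercepts are a valid model.** They are. They are unbiased under randomisation, and using them is not an error. The point is efficiency.

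**Conclusion.** The point holds as a small overstatement of power together with a free improvement. At 115 per arm with the plan's attrition, the slope and year-2 tests have 78.5 to 78.8% power with arm-specific intercepts, 1 to 1.5 points below the stated 80%. A common baseline mean gives 81.9 to 82.5%, a gain of about 3.5 points.

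The figures assume monotone dropout at random, 81% retained at year 2, known variance, and the mean of both breasts as the response, as in section 12.5.

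The constraint itself is sound. Section 12.3 randomises women only after all screening assessments, which include the mammogram, so any baseline difference between arms is due to chance.

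A reader might also conclude that the trial is seriously underpowered because the 2-df test in section 12.4 has lower power. Section 12.5 did not power that test, and it has only about 71% even with 100 complete women per arm. That follows from the choice of test, not from attrition, and is no part of this point.

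**What to change.** - **Section 12.4:** in the primary mixed model, replace the arm-specific intercept with one baseline mean shared by both arms. Treatment then enters only through its interactions with the t1 and t2 indicators, or with time in the linear model. The arm-specific version can be kept as a sensitivity analysis, and observed baseline density can still be tabulated by arm.
- **Section 12.5:** state that, with 10% attrition at each annual visit, 115 women per arm give about 82% power with the common baseline mean (about 79% if arm-specific intercepts are kept). Name the test meant, slope or year-2 contrast, and give the attrition method.
- **Sections 12.2 and 12.5:** reconcile 230 evaluable subjects with 230 women at t0, using the definition in section 10.0.

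This needs no extra women, visits or readings. The cost is wording in the analysis plan, which should be settled before unblinding. The model no longer estimates a baseline difference between arms, which randomisation makes redundant.

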differences at t1 and t2, and their significance tested using a 2-df chi-square test. Low dose tamoxifen will be considered effective if 1) the 2-df test is significant and the expected RTMBD is lower both at t1 and t2 or at t2 compared to that of the placebo group, or 2) the interaction term at t2 is significant and the expected RTMBD there is lower than that of placebo. It should be noted that because common fixed effects for intercept and time coefficients are assumed for both breasts, the expected RTMBD is the same for both breasts within a treatment group. This model enables use of the data from both breasts to estimate the common treatment effect while accounting for the between-breast correlation and the correlation among repeated measurements over time within a woman. The validity of these restrictions, e.g. common intercept and treatment effect between left and right breast, while biologically reasonable, will be examined and tested. This method also enables women with incomplete RTMBD data, i.e. data from only one breast or missing data at specific time points, to be included in the analysis. In addition to the unstructured mean model, we will also fit a linear model in time, with an interaction of time by group indicator to allow for treatment difference. A significant time by group interaction, with a larger negative slope for the low dose tamoxifen group compared to placebo, will indicate the effectiveness of low dose tamoxifen in reducing MBD.

In addition to unadjusted analyses which are appropriate under the randomization principal, adjusted analysis also will be performed. Significantly imbalanced covariates and covariates known to be prognostic for BC, such as radiation dose, age at irradiation, premature menopause, and family history for BC, will be incorporated in the longitudinal models before including and testing the time by treatment group interaction.

To address potential noncompliance, we will also conduct an as-treated analysis, considering patients' actual treatment uptake. Instead of the treatment indicator (PBO or LDTAM), we will include adherence rate, i.e. 0 for PBO and a number between 0 and 1 for LDTAM determined by pill count, in the LME model. Time-specific adherence rate and the overall adherence rate will be considered. If LDTAM is effective, we may expect to see a decrease in MBD with adherence rate.

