The estimates from linear mixed effects model are valid in the presence of incomplete response data if missing data occurs at random. However, non-participation and dropouts may occur differentially between treatment groups for various reasons, possibly resulting in non-ignorable missing data. In addition to collecting information on reasons for nonparticipation, we will apply two analytic approaches to examine the effects of missing data on study results [104]: 1) pattern mixture models and 2) selection models. In pattern mixture models, the four possible missing data patterns (arising from 3 time points with no missing data at t0 and considering a response as missing if data from both breasts are missing) will be used as covariates in the above-described bivariate linear mixed effects model. The effects of missing data on the estimate of treatment effect can be assessed. An overall estimate of the treatment effect may be obtained by averaging the estimates over the missing pattern groups. In selection model, we will model the probability of dropout using baseline covariates to estimate the propensity for dropout. The propensity scores will be used as a covariate in the bivariate linear mixed effects model to adjust for the effects of dropout on treatment effects.

Secondary efficacy objectives will be evaluated by applying the methods for longitudinal analysis as described below. Significance of the low dose tamoxifen effects is evaluated in the manner described above based on testing the significance of the interaction of time by group indicator variables. The distribution of continuous variables will be

examined graphically and appropriate transformations made before applying analytical methods based on normal assumption.

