**Cytomorphology and proliferative index.** Samples for cytomorphology and proliferative index will be collected at two time points, at pre-treatment (t0) and at post-treatment (t2). The Masood score for cytomorphology ranges from 6 to 24, which can be classified into 4 groups of worsening morphology: 1) nonproliferative (6-10), 2) hyperplasia without atypia (11-14), 3) hyperplasia with atypia (15-18), 4) malignancy (19-24). A patient is considered to have cellular atypia if their Masood score is 15 or above. We will compare the effects of low dose tamoxifen versus placebo on changes in Masood score between pre- and post-treatment. Masood score will be treated as a continuous variable, transformed to normality as appropriate, and the linear mixed effects model applied using an indicator variable for pre- and post-treatment time points. We will also consider Masood score as an ordinal outcome with 4 categories and as a dichotomous outcome (cellular atypia or not), and apply the generalized linear mixed model (GLMM) for non-normal data [105].

Proliferative index, defined as the number of cells with unequivocal nuclear staining (Ki-67 expression) out of a total number of ductal epithelial cells contained in RPFNA samples, will be analyzed using longitudinal logistic regression with two time points. If cell counts are better approximated by a Poisson distribution, we will apply the longitudinal Poisson regression method.

**Insulin growth factors.** Insulin growth factor-1 (IGF1) and insulin growth factor binding protein-3 (IGFBP3) will be treated as continuous measures. We will apply the linear mixed effects model for between group comparisons of measures from the three time points. The unstructured mean model and linear in time model will be employed.

***Aim 2:** To establish safety and tolerability of low-dose tamoxifen.*

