Tissue and blood biomarkers: Masood score (cytomorphology) and Ki67 expression (proliferative index) evaluated from breast tissue samples will be obtained at t0 and t2. Insulin growth factors (IGF1 and IGFBP-3) will be measured at 3 time points. With a baseline sample size of 115 women per arm (assuming 10% yearly attrition), assuming Type I error=0.05, 2-sided test, and a within-person correlation of 0.5 between pairs of normally distributed measurements, there is 80% power to detect an effect size of 0.34 (absolute difference between treatment and control means divided by the common standard deviation) at year 2. A similar effect size is detectable for Ki67 for which the problem was formulated as that of detecting the difference at t2 in percent of women with positive expression (at least one cell expressing Ki67) between the treatment groups. Kahn et al [86] reported a median Ki67 expression level of 1.4% in RPFNA samples collected from 147 women at high risk for breast cancer. Thus, we hypothesized that 50% (conservative estimate) to 85%.of our cohort will have Ki67 expression in their healthy breast tissue samples collected via RPFNA at their baseline visit.

Detectable values for the various outcomes are shown in the table below. Column 2 shows the assumed common mean ( $\pm$  SD) at t0 for both treatment groups (obtained from the literature, adjusted for the age structure of our cohort, if possible). Column 3 shows the minimum detectable level at t2 for the tamoxifen group in the hypothesized

direction. The mean levels at t2 in the placebo group are assumed to remain the same as those at t0. Column 4 shows the detectable % change at t2 relative to t0 in the tamoxifen group.

Outcome	Assumed levels at t0 for Placebo and Low dose Tamoxifen groups	Detectable levels at t2 (80% power) for Low dose Tamoxifen group	
	Mean ± SD	Mean	% change (from t0)
Masood score 	14 ± 1.8	13.4	4% ↓
Women positive for Ki67 expression  (%)	50%	32%	36% ↓
	65%	47%	28% ↓
	85%	70%	18% ↓
IGF1  (ng/ml)	260 ± 82.5	230	12% ↓
IGFBP-3  (ng/ml)	3346 ± 1226	3787	13% ↑

Thus, we expect to be able to detect a 5-36% difference in the BC risk biomarkers proposed as secondary endpoints.

**Aim 2:** *To establish safety and tolerability of low-dose tamoxifen.*

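### The stated 80% power at 0.34 SD for secondary biomarkers is 77–79%, or about 67%, depending on a baseline choice the plan leaves open; the tissue-marker power is out of date

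*Combined protocol and SAP*

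**What the plan says.** **Power.** Section 12.5 (Aim 1, tissue and blood biomarkers) states that "there is 80% power to detect an effect size of 0.34" at year 2, where the effect size is the difference in means over the common SD. The inputs are 115 per arm at baseline, 10% yearly attrition, two-sided 5% and a within-person correlation of 0.5. Below its table it concludes: "Thus, we expect to be able to detect a 5-36% difference in the BC risk biomarkers proposed as secondary endpoints". The safety-biomarker paragraph under Aim 2 reuses the figure: "With the proposed sample sizes, the detectable effect size (described earlier) is 0.34".

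**Model.** Section 12.4 writes out one mixed model in full, for mammographic breast density (MBD). In it, "The fixed effects intercept will be allowed to differ between treatment groups". Success can come by two routes. The first begins "Low dose tamoxifen will be considered effective if 1) the 2-df test is significant" and requires the right direction; the second is a significant year-2 interaction in favour of tamoxifen. For secondary efficacy objectives, Section 12.4 takes the longitudinal methods from the text that follows it and says that significance "is evaluated in the manner described above based on testing the significance of the interaction of time by group indicator variables". The text that follows says of the IGFs: "We will apply the linear mixed effects model for between group comparisons of measures from the three time points". It does not say whether the arms share a baseline mean. The power section itself starts, for MBD, from this premise: "Because of randomization, we expect no difference between the expected values of Y at t0 between treatments". For the safety biomarkers, Section 12.4 (Aim 2) names the same mixed models but no specific test and no baseline handling.

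**Tissue sampling.** Section 9.2 limits RPFNA to consenting patients at participating sites. Section 11.2 and study calendar footnote b end it for new patients with the 3/9/2015 version and for everyone on 10/26/15. The Schema says it is no longer collected. Section 12.5 still powers Masood score and Ki67 on 115 per arm.

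**Adverse events.** Section 12.5 claims at least 80% power by Fisher's exact test for 0.5% versus 9.1% with 94 per arm at a 5% level, without saying one- or two-sided.

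**The concern.** The detectable effect depends heavily on whether the model estimates a separate baseline mean for each arm or a single one. At correlation 0.5, a separate baseline raises the variance of the year-2 contrast by a third (a factor of 1 against 0.75, per the formulas below). Section 12.5 gives one figure without naming the model, and Section 12.4 does not settle the model for these markers.

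Objectives 1.1 and 1.2 name the IGFs, lipids, clotting factors and bone markers. A null result on any of them would be read against a stated 80%. If the analysis has less, a null says less than the plan implies, and the choice of baseline handling would be made after the data are in. For the tissue markers, the stated sample no longer describes the trial.

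**Working it through.** **Inputs** (Section 12.5): n = 115 per arm; attrition 10% per year, so 115, 103.5 and 93.15 per arm at t0, t1 and t2; correlation ρ = 0.5, taken as compound symmetry; SD = 1; two-sided 5%. The detectable effect at 80% power is (1.960 + 0.842) × SE = 2.802 × SE. Power is Φ(d/SE − 1.960).

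**Formulas for the year-2 contrast without missing data**
- Arm-specific intercepts: SE = √(4(1 − ρ)/n)
- Common baseline, unstructured means: SE = √(2(1 − ρ²)/n)

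**Step 1: the plan's primary figure.** Section 12.5 uses ρ = 0.8, 100 per arm, no attrition, and states 0.25 SD. Arm-specific: SE = √(0.8/100) = 0.0894, detectable 0.251 SD. Common baseline: SE = √(0.72/100) = 0.0849, detectable 0.238 SD (0.237 in the linear model). The primary figure matches arm-specific intercepts.

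**Step 2: where 0.34 can come from.** Change only ρ to 0.5, still 100 per arm without attrition. Arm-specific: √(2/100) = 0.1414, detectable 0.396 SD. Common baseline: √(1.5/100) = 0.1225, detectable 0.343 SD (0.338 in the linear model). So 0.34 is reproduced by a common baseline on 100 per arm without attrition. That origin is inferred, since the plan names no formula.

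**Step 3: the stated inputs, with attrition.** Generalised least squares over the three monotone dropout patterns gives:

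| Model | SE | Detectable at 80% | Power at 0.34 | Power at 0.36 |
|---|---|---|---|---|
| Arm-specific, unstructured means | 0.1424 | 0.399 | 66.6% | 71.5% |
| Arm-specific, linear in time | 0.1422 | 0.398 | 66.7% | 71.6% |
| Common baseline, unstructured means | 0.1262 | 0.354 | 76.9% | 81.4% |
| Common baseline, linear in time | 0.1233 | 0.345 | 78.7% | 83.1% |

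For example, 0.34/0.1424 − 1.960 = 0.428 and Φ(0.428) = 0.666. A baseline-adjusted comparison of the 93.15 completers per arm has SE √(1.5/93.15) = 0.1269 and power 76.4%, close to the common-baseline rows.

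**Step 4: effect sizes in the tables.** Dividing each tabled difference by its SD:
- Masood 0.6/1.8 = 0.333; TC 15.3/45 = 0.340; AT-III 4.5/13.3 = 0.338; BSAP 1.5/4.5 = 0.333; NTX 5.5/16.1 = 0.342. All fit 0.34 after rounding.
- IGF-1 30/82.5 = 0.364; IGFBP-3 441/1226 = 0.360. These do not.

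**Step 5: tissue markers.** The Ki67 rows fit a two-proportion comparison on 115 per arm without attrition (78–80% power); on 93 per arm they have 69–71%. The number of paired samples is not in the documents, so actual power cannot be computed. The 36% in the summary range is a Ki67 row.

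**Step 6: adverse events.** Exact enumeration for 0.5% versus 9.1%: at 94 per arm, 75% two-sided and 86% one-sided; at 115 per arm, 87% two-sided.

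**The case against.** **The 67% rests on a cross-reference.** A reader might infer that the plan contradicts itself and that true power is 67%. The documents do not support that. Section 12.4 takes the secondary models from the text below, where no intercept is stated, and only the significance rule from above. A common-baseline model also tests time by group. This objection stands, and 67% is one reading. It is not an arbitrary one, because the plan's own primary figure reproduces with that structure. On the other reading, the shortfall from 80% is only 1 to 3 points.

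**Other analyses can reach 80%.** A time-averaged group difference on 93 per arm has 81% at 0.34 SD, but that is neither a year-2 effect nor a time-by-group test. By simulation, the two-route success rule has 69% (effect building linearly) to 78% (full effect by year 1) with arm-specific intercepts, and 79% to 89% with a common baseline. It therefore passes 80% in one configuration, but it declares benefit under no effect in 3.8% of trials against a nominal 2.5% in that direction. Section 12.5 does not invoke it for these markers.

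**The correlation is assumed.** With arm-specific intercepts, 0.34 SD reaches 80% at a correlation of about 0.62 to 0.64, and 0.36 SD at about 0.60. True, but the plan's claim is stated at 0.5.

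**Safety markers.** It is tempting to apply 67% to them too. Section 12.4 names no interaction test there, so that would be an inference.

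**Adverse events.** A reader might call this claim wrong. It is mainly incomplete: it holds one-sided at 94 per arm, and two-sided if all 115 are analysed. Section 10.0 says toxicity status will be reported for all eligible subjects.

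**Tissue sampling was openly stopped.** It was, so no one is misled about sampling; only the power text is stale.

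**Conclusion.** On Section 12.5's own inputs, no planned single-degree-of-freedom year-2 or slope test reaches 80% at 0.34 SD. Power is 77–79% (about 0.35 SD detectable) with a common or adjusted baseline, and about 67% (about 0.40 SD) if arm-specific intercepts are carried over. The plan does not say which applies. The result assumes compound symmetry, monotone dropout and a correlation of 0.5.

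Two further errors need no modelling choice. The IGF rows are at 0.36 SD instead of the stated 0.34, and the Masood and Ki67 claims rest on a sample that cannot be 115 per arm. The sidedness of the adverse-event test is a minor omission.

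The practical size is modest: even at 0.40 SD, IGF-1 moves from 230 to 227 and IGFBP-3 from 3787 to 3836. The primary endpoint and the 230-patient sample size are not affected.

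**What to change.** 1. **Preferred.** Add one sentence to Section 12.4 prespecifying a common baseline mean, or adjustment for the baseline value, for the IGFs and other continuous markers. In Section 12.5 state 77–79% power at 0.34 SD, or about 0.35 SD at 80%. The IGF rows become 260 − 0.35 × 82.5 = 231 (11%) and 3346 + 0.35 × 1226 = 3775 (13%). The safety range stays 5–23%.
2. **If arm-specific intercepts are kept.** State about 0.40 SD: IGF-1 260 − 33 = 227 (13%) and IGFBP-3 3346 + 490 = 3836 (15%). Recompute the safety rows (TC 217, AT-III 94.7, BSAP 5.9, NTX 18.0; range 5–26%) only if the same interaction test is confirmed for them.
3. Under either option, put the IGF rows on the same effect size as the other continuous rows.
4. Withdraw the 80% claim for Masood and Ki67 and the 5–36% range, and restate both on the actual number of paired RPFNA samples.
5. State the sidedness and the analysis set for the adverse-event test, with the matching power.

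The cost is text and table edits. No patients or visits are added.
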